## 5 INVESTIGATIONAL PRODUCT INFORMATION

### 5.1 COVID-HIGIV

#### 5.1.1 Packaging and Formulation

COVID-HIGIV is a sterile liquid preparation of purified human immunoglobulin (IgG) fraction containing SARS-CoV-2 antibodies. The final product contains 85-115 mg/mL of human plasma proteins (target 100 mg/mL), of which at least 90% is human IgG. COVID-HIGIV is formulated with 250 mM proline and 0.03% (w/w) PS80 and has a pH between 5.5 and 6.0 (target pH 5.8). The final product contains no preservatives.

The final COVID-HIGIV product will be supplied in 50 mL Type 1 glass vials sealed with 20 mm siliconized bromobutyl rubber stoppers, aluminum seals, and plastic flip-off caps. The extractable volume per vial is 25.0 mL. Each vial is intended for single use. The vials will be provided in shelf cartons (4 vials per shelf carton).

For more information, please refer to the most current version of the Investigator's Brochure for COVID-HIGIV.

#### 5.1.2 Labeling

COVID-HIGIV vial and shelf carton labels will include information that will comply with US regulations, in the appropriate language(s).

For dispensing labels for secondary receptacles, refer to Section [5.1.5](#).

#### 5.1.3 Shipment

COVID-HIGIV will be shipped to the site at a temperature of 2-8°C (35-46°F). During shipment, the temperature will be monitored to ensure the required temperature conditions are maintained. The site pharmacist or designate will be responsible for checking the number of vials and the condition of the vials received and entering this information into the drug accountability records, reporting the condition to Emergent or designate. The site pharmacist or designate will be responsible for assessment of the shipping temperature including upload of temperature data from the electronic temperature monitoring device, as well as returning of the shipping container and all required documentation to Emergent or designate. Study treatment will be released for use by the site only after the data logger results are reviewed and written authorization has been issued to the investigator/designate by Emergent. Temperature excursions during shipment must be reported to Emergent as per instructions provided in the Pharmacy Manual.

At the end of the study, or upon request of Emergent, all unused, partially used or empty vials will be returned to Emergent or destroyed at the site as directed by Emergent.

### 5.1.4 Storage Conditions

Once at the site, COVID-HIGIV vials must be stored at 2-8°C (35-46°F) in a secured area until used for dose preparation by the assigned pharmacy staff. The temperature in the storage area should be monitored with properly calibrated instruments and recorded on a temperature log. Temperature excursions must be reported to Emergent or designate as per instructions provided in the Pharmacy Manual.

For further information, refer to the COVID-HIGIV Investigator's Brochure and the Pharmacy Manual.

### 5.1.5 Preparation

The site must maintain documentation of a clear written formalized procedure for study drug preparation activities (including any sample labels and documentation to be completed), and documented training and delegation of the activity to appropriate study staff.

Subject identifier (subject ID number) must be recorded on the labels of the vial(s) used to prepare the dose. The unblinded pharmacy staff assigned to this study will prepare COVID-HIGIV as follows:

Visually inspect the vials to ensure the product is free from particulate matter and discoloration prior to dose preparation and administration. The solution should be clear or slightly opalescent and colorless or pale yellow. **Do not use solutions that are cloudy or have particulates. DO NOT SHAKE VIALS; AVOID FOAMING.**

Prepare COVID-HIGIV at the required dosage into an IV infusion bag (note: all doses are to be prepared to maximum volume of 400 mL; refer to Pharmacy Manual for details around dose preparation). In general, perform the following:

- Remove the protective caps from the product vials.
- Wipe the exposed central portion of the rubber stopper with an isopropyl alcohol swab.
- Withdraw the vial content (note: extractable volume is up to 25.0 mL per vial) into a sterile syringe (that can accommodate up to 25.0 mL) using standard aseptic techniques and transfer the content into an appropriately sized and labeled IV infusion bag.
- If multiple transfers of content from COVID-HIGIV vials are needed to prepare the total dose in the IV infusion bag, use aseptic techniques to prevent contamination.

Once punctured, use the vial contents to prepare the infusion bag promptly. COVID-HIGIV contains no preservative. Vials are for single use only. **Do not reuse or save vial(s) for future use.**

Retain used and empty vials for drug accountability as per instructions in the Pharmacy Manual.

The IV infusion bag for COVID-HIGIV (and placebo) requires that the dispensing label is affixed to the bag. The label on the IV infusion bag will capture at a minimum: subject ID, expiry date of the prepared dose (i.e., <24 hours after dose preparation), the investigator's name, protocol code (EBS-CVH-003) and caution statement "For investigational use only". The IV

infusion bag will require a cover to maintain the blind. Protective coverings for the IV infusion bags will be provided by Emergent as part of the study materials.

Record date of the infusion, start/stop times and the total volume infused. For further details, refer to the Pharmacy Manual.

### **5.1.6 Administration**

Ensure the recipient is adequately hydrated prior to initiation of IV infusion.

Administer COVID-HIGIV by IV infusion through a dedicated IV line using a constant infusion pump (e.g., IVAC® pump or equivalent).

Administer COVID-HIGIV within 24 hours of preparation into an IV infusion bag.

Set the starting infusion rate at 1.0 mL/min for the first 30 minutes. If the infusion is well tolerated, double the infusion rate to 2.0 mL/min for the next 30 minutes, and if tolerated, double the rate to 4.0 mL/min (maximum rate) which should be used for the remainder of the infusion.

For example, at the recommended infusion rates above (with no interruptions or reduction in the infusion rates), dose volume of 400 mL should be infused within 2.5 hours.

Monitor subjects closely during infusion and within 24 hours after completion of COVID-HIGIV infusion.

If AEs occur during the IV infusion, such as grade 1 (mild) events of flushing, headache, chills, fatigue, nausea, slight changes in pulse rate or blood pressure, slow the rate of infusion or temporarily stop the infusion until symptoms subside (at discretion of the investigator). Once the AEs resolve, resume the infusion at a rate that is comfortable to the subject (e.g., start the infusion at half of the last tolerated infusion rate and increase gradually). If the recipient experiences grade 2 (moderate) or higher AEs such as chest pain, difficulty breathing, vomiting, arthralgia, or severe headache, unresponsive to slowing the infusion rate or stopping of the infusion, do not resume the infusion.

Stop the infusion if serious AEs develop (e.g., anaphylaxis, severe hypersensitivity reactions) and administer appropriate medical management. Do not restart the infusion.

### **5.1.7 Drug Accountability**

The investigator is responsible for maintaining accurate inventory records of COVID-HIGIV. The pharmacist or pharmacy staff designate will inventory all COVID-HIGIV shipments upon receipt, acknowledge possession by signing all required documentation, and returning these to the sponsor. The investigator must ensure that all drug supplies are kept in a secure location in the site pharmacy in accordance with recommended storage conditions. A site pharmacist (unblinded) or a designated individual (unblinded) not involved in study treatment administration/study assessments will maintain a current inventory and ongoing record of test material supplies using the Drug Accountability Form provided by the sponsor. This inventory record for the COVID-HIGIV will include:

- Protocol name, number and sponsor

- Product name and description
- Study site and investigator name
- Product lot number and date of manufacture and/or Use-by/Expiry/Re-test date
- Number of vials dispensed, date and time of dispensing and study subject for whom product was dispensed
- Product balance
- Name and title of qualified individual dispensing product.

These records will be reviewed by unblinded representatives contracted out by the sponsor and may be reviewed by regulatory agencies.

## **5.2 Description of Reference Treatment, Comparator and/or Placebo**

This study is not using a reference treatment or a comparator; rather a placebo control will be used. The intended placebo is a normal saline (0.9% w/v sodium chloride) liquid solution suitable for IV administration. In general, placebo will be prepared at the same volume as COVID-HIGIV doses, and administration of placebo will be the same as for COVID-HIGIV (e.g., IV infusion, starting infusion rates/incremental increases in infusion rates). Refer to the Pharmacy Manual for details on the placebo.

## 6 STUDY PROCEDURES

### 6.1 Screening

Screening period is within seven days prior to Day 1.

Eligible subjects will first undergo informed consent counselling. Once informed consent has been obtained, subjects will undergo a screening visit in the clinic to ascertain their eligibility for the study.

Perform the following screening visit assessments:

- Informed consent.
- Eligibility.
- Collection of demography information (age, gender, race/ethnicity, height, body weight, BMI).
- NP swab sample for SARS-CoV-2 point-of-care RT-PCR test.
- Medical history and ongoing medications.
- Complete physical exam (to include assessment of general appearance, and the following body systems: head/eyes/ears/nose/throat, respiratory, cardiovascular, gastrointestinal, dermatological, lymphatic/hematological, musculoskeletal, neurological, metabolic/endocrine).
- For WOCBP: instruct on use of contraception from the time of Screening through end of study period (up to Day 85 visit).
- Vital signs including body temperature, blood pressure (seated), pulse, SpO2 (pulse oximetry) and respiratory rate.
- Safety laboratory assessments:
  - Chem 7 panel [sodium (Na+), potassium (K+), chloride (Cl), bicarbonate (HCO3), BUN, creatinine, glucose], total and direct bilirubin, ALT, AST, LDH,
  - CBC (red blood cells, white blood cells, hemoglobin, hematocrit) with differential (neutrophils, eosinophils, basophils, monocytes, lymphocytes).
  - Urinalysis.
- Viral marker testing (HIV 1/2 antibody, HBV surface antigen, HCV antibody).
- SARS-CoV-2 antibody (IgM, IgG) point-of-care rapid test.
- Provide counselling to subjects on precautions/measures to prevent contracting SARS-CoV-2 infection.

### 6.2 Day 1 – Randomization and Dosing

Perform the following assessments on Day 1:

- If WOCBP, perform UPT.
- If required, update medical history and ongoing medications.
- Inquire if the subject has had a suspected or confirmed exposure to SARS-CoV-2 in the period of Screening visit to Day 1.
- Confirm eligibility.
- Vital signs [body temperature, blood pressure (seated), pulse, SpO2 (pulse oximetry) and respiratory rate]; within 2 hours prior to dosing.
- Collect NP swab sample for SARS-CoV-2 point-of-care PCR test.
- Collect pre-dose serum sample (within 4 hours prior to dosing) for SARS-CoV-2 antibody PK assessment.
- Randomize.
- Administer randomized study treatment via IV infusion.
- Monitor/assess AEs during the infusion and after the end of infusion for the time period the subject is in the clinic (i.e., for at least 24 hours after end of the infusion).
- Vital signs [body temperature, blood pressure (seated), pulse, SpO2 (pulse oximetry) and respiratory rate] at 30 minutes ( $\pm 5$  mins) and 1 hour ( $\pm 10$  mins) after end of IV infusion.
- Serum samples for PK assessment of SARS-CoV-2 antibodies at 1 hour ( $\pm 15$  mins), 2 hours ( $\pm 15$  mins), 4 hours ( $\pm 30$  mins), 8 hours ( $\pm 1$  hour) and 12 hours ( $\pm 1$  hour) after end of IV infusion.
- Keep the subject in the inpatient unit overnight (i.e., for 24 hours after end of IV infusion).
- Record any concomitant medications (if applicable).

### 6.3 Post-Dosing Assessments

#### 6.3.1 Day 2 – Discharge

Day 2 (in-clinic visit) will occur 24 hours ( $\pm 2$  hours) after end of IV infusion on Day 1. Perform the following:

- Assessment of AEs and concomitant medications.
- Serum sample for SARS-CoV-2 antibody PK assessment.
- Safety laboratory assessments (chem 7 panel, total and direct bilirubin, ALT, AST, LDH, CBC with differential).
- Urinalysis.
- Vital signs [body temperature, blood pressure (seated), pulse, SpO2 (pulse oximetry) and respiratory rate].

- Targeted physical exam (if clinically indicated).
- Assessment of clinical status based on modified WHO ordinal scale. Note: perform this assessment ONLY if the subject's prior RT-PCR test (i.e., Day 1) returned as positive.
- Remind the subjects of the precautions/measures to prevent SARS-CoV-2 infection.
- Discharge the subject.

### 6.3.2 Days 4, 8, 15, 22, 29, 43 and 57

Visits are conducted as in-clinic or telemedicine/home healthcare follow-ups.

Visit windows are as follows (in relation to end of IV infusion):

Day 4: 3 days $\pm$ 12 hours; Day 8: 7 $\pm$ 1 days; Day 15: 14 $\pm$ 2 days; Day 22: 21 $\pm$ 2 days; Day 29: 28 $\pm$ 2 days; Day 43: 42 $\pm$ 3 days; Day 57: 56 $\pm$ 3 days.

Perform the following in-clinic or via telemedicine follow-up:

- Assessment of AEs and concomitant medications.
- Targeted physical exam, if clinically indicated. Based on the investigator's assessment of adverse events/concomitant medications during telemedicine follow-up, an unscheduled visit (in-clinic) can be arranged to conduct a targeted physical exam. The investigator can also refer the subject to their healthcare provider or urgent care if immediate medical attention is required.
- Assessment of clinical status based on modified WHO ordinal scale and COVID-19 symptoms (if reported). Note: perform the assessments (via a telephone contact) ONLY if the subject became positive at any time post-dosing during the study period.
- Remind the subjects of precautions/measures to prevent contracting SARS-CoV-2 infection.

In-clinic staff or home healthcare attendant to perform the following:

- NP swab sample for SARS-CoV-2 point-of-care RT-PCR test.
- Serum sample for SARS-CoV-2 antibody PK assessment.

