	
 
• Medical history and ongoing medications.
 
• Complete physical exam (to include assessment of general appearance, and the following body systems: head/eyes/ears/nose/throat, respiratory, cardiovascular, gastrointestinal, dermatological, lymphatic/hematological, musculoskeletal, neurological, metabolic/endocrine).
 
• For WOCBP: instruct on use of contraception from the time of Screening through end of study (up to Day 85).
 
• Vital signs including body temperature, blood pressure (seated), pulse, SpO2 (pulse oximetry) and respiratory rate.
 
• Safety laboratory assessments: 
 
• Chem 7 panel [sodium (Na+), potassium (K+), chloride (Cl), bicarbonate (HCO3), blood urea nitrogen (BUN), creatinine, glucose], total and direct bilirubin, alanine aminotransferase (ALT), aspartate aminotransferase (AST), lactate dehydrogenase (LDH),
 
• Complete blood count (CBC); i.e., red blood cells, white blood cells, platelets, hemoglobin, and hematocrit, with differential (neutrophils, eosinophils, basophils, monocytes and lymphocytes).
 
• Urinalysis.
 
 
 
• Viral marker testing [Human immunodeficiency virus 1/2 (HIV 1/2) antibody, Hepatitis B virus (HBV) surface antigen, Hepatitis C virus (HCV) antibody].
 
• Serum PT, if WOCBP.
 
• Serum sample for SARS-CoV-2 antibody (IgM, IgG) point-of-care rapid test.
 
• Provide counselling to subjects on precautions/measures to prevent contracting SARS-CoV-2 infection.
 
 
Randomization/Dosing – Day 1: in-clinic visit.
 
 
• If WOCBP, perform urine pregnancy test (UPT).
 
• If required, update medical history and ongoing medications.
 
• Inquire if the subject has had a suspected or confirmed exposure to SARS-CoV-2 in the period of Screening visit to Day 1.
 
• Confirm eligibility.
 
• Collect NP swab sample for SARS-CoV-2 point-of-care RT-PCR test.
 
• Collect pre-dose serum sample (within 4 hours prior to dosing) for SARS-CoV-2 antibody level assessment.
 

--	---

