**Table 2 Overview of Study Design**

Study Arm	No. of Subjects	Dosing Schedule – Day 1 Visit
1	8	COVID-HIGIV dosage 1*
2	8	COVID-HIGIV dosage 2**
3	8	COVID-HIGIV dosage 3***
4	4	Placebo (saline)

\* 100 mg/kg ( $\approx$ 1 mL/kg), with a maximum of 100 mL COVID-HIGIV for  $\geq$ 100 kg body weight.

\*\* 200 mg/kg ( $\approx$ 2 mL/kg), with a maximum of 200 mL COVID-HIGIV for  $\geq$ 100 kg body weight.

\*\*\* 400 mg/kg ( $\approx$ 4 mL/kg), with a maximum of 400 mL COVID-HIGIV for  $\geq$ 100 kg body weight.

Following randomization and dosing on Day 1, subjects will be kept in the inpatient unit and will be discharged the following day (Day 2 visit). Subjects will be followed for safety and PK up to 84 days (up to Day 85 visit) post-dosing.

Overall study duration for subjects will be up to 91 days (seven days of screening period and 84 days of follow-up post-randomization).

The enrollment/dosing of the first seven subjects (2:2:2:1 randomization) in the study will be staggered, wherein no more than three subjects will be dosed on the same day (dosing at least 1 hour apart). Principal Investigator (PI) and the Sponsor's Medical Monitor (MM) will review blinded data (up to 24 hours after end of IV infusion) before proceeding with dosing subsequent set of staggered subjects. Available safety (blinded) data will be reviewed by Study Monitoring Committee (SMC) (consisting of at least three independent external medical monitors) after seven subjects have completed at least 72 hours of safety follow-up. If unblinding of the safety data is required, closed session by the SMC will be held. An overall decision by the SMC will be made to proceed with full randomization (2:2:2:1) and dosing of the remaining study subjects (n=21). The SMC will perform overall ongoing review of safety data during the study. Study enrollment and administration of study treatments may be temporarily paused by the SMC for safety review, if required (see [Section 8.11](#) for study safety-pausing rules).

Subjects who become positive for SARS-CoV-2 at any time post-dosing follow-up period will be withdrawn from the study (no further specimen collections), but will be followed up for safety only via telemedicine until their originally scheduled last follow-up visit. Subjects who report

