## 4 SELECTION OF STUDY SUBJECTS

### 4.1 Subject Inclusion Criteria

Subjects must meet the following inclusion criteria to participate in the study:

1. Able and willing to provide written informed consent (voluntarily signed by the subject) prior to performing any study procedures.
2. Females or males, 18-60 years of age, inclusive.
3. Body mass index (BMI) less than or equal to 35.0 kg/m^2.
4. Women who are either:
  - A) Not of childbearing potential: surgically sterile (at least six weeks post bilateral tubal ligation, bilateral oophorectomy or hysterectomy), or post-menopausal (defined as  $\geq 50$  years of age with a history of  $\geq 12$  months without menses prior to randomization in the absence of other pathologic or physiologic causes, following cessation of exogenous sex-hormonal treatment); OR
  - B) Women of childbearing potential (WOCBP) who are not planning to be pregnant during the study period and meet all of the following criteria:

Negative pregnancy test prior to randomization/dosing at Day 1; **and**

Use of a highly effective contraception during the study period:

- Hormonal contraceptives (e.g., implants, pills, patches) initiated  $\geq 30$  days prior to Day 1; or
- Intrauterine device (IUD) inserted  $\geq 30$  days prior to Day 1; or
- Double barrier type of birth control (e.g., male condom with female diaphragm, male condom with cervical cap).

5. Subject understands and agrees to comply with planned study procedures.
6. Healthy as determined by principal investigator based on medical history, physical exam, vital signs, urinalysis, blood chemistry and hematology test results at Screening and no evidence of prior exposure to SARS-CoV-2 (i.e., RT-PCR negative for SARS-CoV-2 and negative for SARS-CoV-2 antibodies) at Screening.

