#### **4.3.1 Subject Withdrawal Criteria**

All subjects are free to withdraw from participation in this study at any time, for any reason, specified or unspecified, and without penalty or loss of benefits to which the subject is otherwise entitled. In addition, subjects may be withdrawn from the study for any of, but not limited to, the following reasons:

- The subject develops an intercurrent illness that prevents completion of the study.
- The subject becomes positive for SARS-CoV-2 at any time post-dosing.
- It is the opinion of the principal investigator that it is unwise for the subject to continue in the study.
- The subject is not compliant with the requirements of the study to the satisfaction of the investigator and/or sponsor (e.g., non-cooperative, misses appointments, unreported use of concomitant medications).
- The subject is lost to follow-up.

If a subject is withdrawn from the study, they will not be re-entered into the study for any reason.

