#### **4.3.2 Subject Replacement**

Subjects withdrawn from the study or who withdraw consent after randomization will not be replaced.

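### The pre-dose Day 1 RT-PCR result is not part of eligibility, so a subject already infected at baseline can be randomised and dosed

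*Protocol*

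**What the plan says.** **Entry.** Protocol 4.1, inclusion 6, defines no prior exposure as "RT-PCR negative for SARS-CoV-2 and negative for SARS-CoV-2 antibodies) at Screening". The timing is set in 6.1: "Screening period is within seven days prior to Day 1".

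**Day 1.** Section 6.2 puts the eligibility check first, then "Collect NP swab sample for SARS-CoV-2 point-of-care PCR test", then randomisation and infusion. The synopsis also places "Collect NP swab sample for SARS-CoV-2 point-of-care RT-PCR test" after the eligibility check and before randomisation. Neither list says that the result must be read before randomisation, or what a positive result means.

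**Day 2.** At the discharge visit, 24 hours after the end of infusion, section 6.3.1 qualifies the WHO ordinal scale assessment: "Note: perform this assessment ONLY if the subject's prior RT-PCR test (i.e., Day 1) returned as positive". The synopsis repeats this.

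**After dosing.** Section 4.3.1 lists among the reasons for which a subject may be withdrawn: "The subject becomes positive for SARS-CoV-2 at any time post-dosing". Section 3.1 is firmer: "Subjects who become positive for SARS-CoV-2 at any time post-dosing follow-up period will be" withdrawn from further sampling, with safety follow-up by telemedicine. SAP 2.2 says that such subjects may be withdrawn. Section 4.3.2 adds: "Subjects withdrawn from the study or who withdraw consent after randomization will not be replaced".

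**Analysis sets.** The Safety Set (protocol 9.2, SAP 5.2) keeps every randomised subject who receives any study treatment. The PK Set has no rule on baseline RT-PCR. SAP 8.5.2 allows, but does not require, exclusion or background subtraction for anomalous pre-dose antibody concentrations.

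**The concern.** The stated population is healthy adults with no evidence of SARS-CoV-2 exposure, and both primary objectives concern healthy adults. The one test that shows infection status at the moment of dosing is collected but does not decide entry.

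Three things are at stake. Illness that starts or worsens after infusion meets the AE definition and is tabulated in an arm of eight or four. The subject's own antibody response may develop during PK sampling. And the randomisation slot cannot be recovered, whereas a subject stopped before randomisation uses none.

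A Day 1 positive also falls between the later rules. Withdrawal, WHO-scale follow-up after Day 2, and the planned COVID-19 summaries (protocol 9.6.2, SAP 9.6 and 9.7) are all written for subjects who become positive after dosing.

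**Working it through.** **1. The plan's own figure.** SAP 2.3.1 gives blocks of seven at 2:2:2:1. With 28/7 = 4 blocks, the arms are 4×2 = 8, 8 and 8, and 4×1 = 4, total 28. This reproduces the planned size. There is no power calculation to check, and this point does not challenge the 28.

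**2. Does the text admit a dosed subject with a positive baseline swab?**

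| Place | RT-PCR result required before randomisation? |
|---|---|
| Inclusion 6 | Screening only |
| 6.2 and synopsis, Day 1 | Swab collected after the eligibility check; no rule on the result |
| 6.3.1 and synopsis, Day 2 | Assessment planned if the Day 1 result was positive |
| Table 1 footnote 10 (also SAP Appendix I), attached to Day 2 | Assessment only if positive after dosing |

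Table 1 schedules no swab on Day 2, and the Day 1 swab is listed before dosing. A scheduled swab therefore cannot meet the footnote 10 condition on Day 2. The Day 2 note and the footnote contradict each other, and the note provides for a subject who was positive before dosing and was dosed.

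The Day 1 pregnancy test is handled differently. Inclusion 4 requires it to be negative before randomisation or dosing, 6.2 lists it ahead of the eligibility check, and Table 1 footnote 8 places it before randomisation. RT-PCR has none of these.

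**3. Would the pre-dose antibody check find the subject?** Protocol 1.1.1 puts incubation at about 4-5 days (range 2-7) and detectable IgG at about 14 days after symptom onset (range 5-18). Someone infected between Screening and Day 1 may well be antibody-negative pre-dose, so SAP 8.5.2 can miss them.

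**4. Share if it happens.** 1/8 = 12.5% of an active arm; 1/4 = 25% of placebo; 1/7 = 14.3% of the first SMC review.

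**5. Chance that it happens.** The documents give no incidence. Let p be the assumed daily chance of newly detectable infection and g the mean gap from Screening to Day 1. The chance of at least one among 28 is 1 − (1 − p)^(28g).

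| p (assumed) | g = 3.5 days (98 subject-days) | g = 7 days (196 subject-days) |
|---|---|---|
| 0.01% | 1.0% | 1.9% |
| 0.1% | 9.3% | 17.8% |

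**6. PK consequence for one active arm.**
- *Subject lost from PK.* The log-scale 95% CI half-width is t(0.975, n−1)/√n in SD units. For n = 8 it is 2.365/√8 = 0.836, and for n = 7 it is 2.447/√7 = 0.925. The interval is 10.6% wider.
- *Subject kept.* If their own response raises a PK value f-fold, the arm's geometric mean rises by the factor f^(1/8). For f = 2 this is 1.091 (9%), and for f = 10 it is 1.334 (33%). Both values of f are assumed.

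**The case against.** The strongest reply is that silence is not an instruction. The test is point-of-care and is listed before randomisation. Day 1 includes an exposure inquiry. Exclusion 15 (a medical condition that raises risk) and exclusion 17 (the investigator thinks randomisation unwise) both allow refusal. Bullet order is weak evidence, because the pre-dose vital signs sit in different places in 6.2 and the synopsis, and randomisation details are left to a Pharmacy Manual outside these documents. The Day 2 note may be a drafting remnant or a provision for a late result.

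Much of this stands, and it rules out several stronger readings that a reader might infer:

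- *That the protocol orders such a subject to be dosed, or that the subject meets every entry criterion.* It permits dosing, and exclusions 15 and 17 give discretion to stop it.
- *That withdrawal cannot reach this subject.* The list in 4.3.1 is expressly not exhaustive and includes the investigator's opinion. A swab still positive on Day 4 might also be handled under 3.1.
- *That one subject's COVID-19 symptoms would trip the pause rule.* Section 8.11 needs an SAE, three of the same grade 3 event or five of the same grade 2 event, and then the SMC may pause. One subject could realistically do this alone only through an SAE. Protocol 1.1.1 gives 81% mild disease, 8.1.1 prefers one unifying diagnosis to separate symptoms, and conditions already present before dosing go to medical history.
- *That 18% is the expected risk.* It needs the upper assumed incidence and a full seven-day gap for all 28 subjects.

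None of these answers makes the Day 1 result a condition of entry. They are discretionary or act only after dosing. The argument does not rest on bullet order alone: inclusion 6 names Screening only, no section gives the Day 1 result a consequence before dosing, and the Day 2 note has a use only if a Day 1 positive has been dosed.

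**Conclusion.** The concern holds in this form: the plan collects a pre-dose RT-PCR result on Day 1, does not make it part of eligibility, and so lets a subject outside its stated population take a slot that will not be refilled. Inclusion in the Safety Set is then certain. Inclusion in the PK Set is open, because later withdrawal or an anomalous pre-dose antibody value could remove data, though the antibody check may miss a recent infection.

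The size if it happens is 12.5% of an active arm or 25% of placebo, in a descriptive study. The probability is not in the documents; about 1% to 18% for at least one of 28 rests wholly on the assumed incidence and gap. The PK effects (a 10.6% wider interval if the subject is lost, a 9% to 33% shift if kept) are conditional on such a subject occurring in that active arm, and the shift also on an assumed 2- to 10-fold rise.

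**What to change.** - In 6.2 and the synopsis, list the Day 1 swab and the reading of its result before the eligibility check and randomisation.
- Align inclusion 6 with the stated population by referring to the Day 1 pre-randomisation result as well as Screening, so that a subject found ineligible uses no randomisation slot.
- Reconcile the Day 2 note (6.3.1 and synopsis), footnote 10 (Table 1 and SAP Appendix I) and the withdrawal text (protocol 3.1 and 4.3.1, SAP 2.2) on the status of any subject whose Day 1 result is positive or arrives late. The note should not simply be deleted, since a late result could still occur.
- State the analysis-set status of such a subject in protocol 9.2 and SAP 5.2.

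The swab is already collected and is point-of-care, so the cost is wording, a short wait on Day 1 and an occasional late screen failure. The planned 28 (8/8/8/4) does not change.
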